5.1 Primary Outcomes

The primary outcome is pain interference at 12-months measured using the BPI interference sub-scale. The BPI was measured at baseline, 3-, 6-, 9-, and 12-months. The BPI interference subscale includes seven numeric ratings of pain interference with general activity, mood, walking, work, relations with other people, sleep and enjoyment of life and is scored as the average of the individual item scores.^{7,8}

5.2 Key Secondary Outcomes

Secondary outcomes include the BPI pain intensity, functioning/quality of life (Veterans Rand 12-Item Health Survey), use of pain medications (including opioids if applicable) from VA administrative data (corroborated by self-report), and number of non-pharmacological pain self-management activities. Past-year of use of complementary integrative health (CIH) therapies and self-management practices were measured using the Nonpharmacological and Self-Care Approaches developed by the PMC (NSCAP).⁹

5.3 Additional Secondary Outcomes

Additional secondary outcomes include total BPI and co-morbid mental health-related symptoms. The mental health symptoms were measured using validated brief measures: the Patient Health Questionnaire (PHQ-9) and the General Anxiety Disorders questionnaire (GAD-7) measured depression and anxiety, respectively;¹⁰ the PHQ-9 was used to screen for suicidality; the primary care PTSD screen assessed PTSD-related symptoms;¹¹ Tobacco, Alcohol, Prescription medication and other Substance (TAPS) Tool;¹² and AUDIT-C¹³ measured alcohol and substance abuse; and the PROMIS – Sleep Disturbance¹⁴ measure assessed sleep and fatigue. The Patient Global Impression of Change Scale (PGIC) was used to assess change in overall status during the study.

5.4 Safety Outcomes

An **adverse event (AE)** is generally defined as any unfavorable and unintended diagnosis, symptom, sign (including an abnormal laboratory finding or passive suicidal ideation), syndrome, or disease that either occurs during the study, having been absent at baseline, or if present at baseline, appears to worsen. Adverse events are recorded regardless of their relationship to the study intervention.

When an adverse event occurs, study coordinators will document information regarding the event in the study application event log. Coordinators will also complete an AE form in RedCap and save the downloaded PDF to their site's regulatory binder. Study coordinators will alert the overall trial project manager to all AEs that occur during the trial. AEs that are unanticipated problems involving risks to subjects or others will be reported promptly to the VA Central IRB (CIRB) within five business days. AEs that do not meet criteria for reporting within five days in accordance with VHA Handbook 1058.01 will be reported to the CIRB annually at Continuing Review.

A **serious adverse event (SAE)** is generally defined as any untoward medical occurrence that results in death, is life-threatening, requires inpatient hospitalization or prolongation of existing hospitalization, or results in persistent or significant disability/incapacity. In the case of the wHOPE study, this could include an opioid overdose, for example.

When an SAE occurs, study coordinators will document information regarding the event in the study application event log. Coordinators will also complete an SAE form in RedCap and alert the overall trial project manager, Site PI, and a lead PI (Drs. [name] or [name]) of the event. After reviewing the SAE form, the site PI and lead PI will sign the form and the coordinator will save the signed PDF to their site's regulatory binder. All SAEs are reported biannually to the DSMB. Serious unanticipated problems involving risks to subjects or others, and unanticipated SAEs will be reported promptly to the CIRB within five business days. SAEs that do not meet criteria for reporting within five days in accordance with VHA Handbook 1058.01 will be reported to the CIRB annually at Continuing Review.

4. Sample Size

The primary outcome is change in BPI interference from baseline to 12-months. Sample size estimates were based on repeated-measures ANOVA assuming two-repeated measures, using the F-test with a focus on the pairwise comparisons. The overall family-wise type I error rate was set at 0.05 with a split of 0.03 for the WHT vs. PC-GE comparison, 0.01 for the WHT vs. UPC comparison and 0.01 for the PC-GE vs. UPC comparison. We assumed a power of 90% for all comparisons. For the comparison between WHT and PC-GE we assumed 1:1 randomization and an effect size of 0.15, which was informed by our prior OPTI study where the correlation between repeated measures was 0.66 and the variance (assuming constant over time) was 5.9. With these assumptions, we determine we would need a sample

size of 273 per arm in the WHT and PC-GE arms. Given the sample size of 273, and assuming an effect size of 0.3, we determine the sample size (using an unequal allocation) needed for the UPC arm to be 50. Assuming a 20% attrition rate, the final sample size was 765 (341 in each of the WHT and PC-GE arms and 83 in the UPC arm).

5. Interim Monitoring

Interim monitoring will focus on patient accrual, baseline comparability of treatment groups, protocol adherence, loss to follow-up, data completeness, quality, and safety. No formal interim look for effectiveness or futility are planned.

6. Data Collection and Data Freeze

Data will be collected using REDCap through primary data collection of patient-reported outcomes. We will use the VHA electronic health record (EHR) to capture selected outcome measures from VA clinical visits (e.g. medications).

Data will be locked one month prior to meeting with the DSMB so that reports can be prepared and distributed to members. The final data set will be locked before conducting any of the proposed analyses.

7. Analytic Plan

7.1 General Considerations

The analysis of the primary and secondary outcomes will be according to the principle of intent-to-treat, i.e., participants will be analyzed according to their original treatment assignment regardless of adherence to the protocol. All analyses will account for the IRGT design and stratification by site, sex, and opioid use. The unit of analysis will be the participant. Three pairwise comparisons will be conducted: WHT vs. PC-GE; WHT vs UPC; PC-GE vs. UPC. SAS version 9.4 and the latest version of R will be used for analyses. Overall, family-wise type I error rates (two-sided) of 0.05 will be considered for both the primary and secondary outcomes split such that 0.03 will be given to the comparison between WHT and PC-GE and 0.01 will be given to each of the comparisons of PC-GE and WHT to UPC.

Comparability of treatment groups will be assessed by comparing the distribution of baseline characteristics in the three groups using appropriate graphical procedures and summary statistics (e.g., means and standard deviations for continuous data; frequencies and proportions for categorical data). The randomization is designed to produce balance on important covariates. Any baseline covariates that appear to be imbalanced between the treatment groups will only be adjusted for in sensitivity analyses.

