## **8.6 Data Analyses**

For the primary analysis, we aim to follow the intention-to-treat (ITT) principle. We will conduct two types of pair-wise comparisons with different alpha levels:

- Two active interventions respectively compared with Usual Primary Care: WHT vs. UPC (alpha=0.01) and PC-GE vs. UPC (alpha=0.01);
- Two active interventions compared with each other: WHT vs. PC-GE (alpha=0.03).

We will use a mixed-effects linear regression using BPI interference score (averaged by the number of items with non-missing values provided that at least 4 of the 7 items were answered, per guidelines) as the outcome for each of the three pair-wise comparisons. We will include intervention, time (6 months and 12 months) and their interaction term, and will report the treatment effect at 12 months. In terms of covariance structure for repeated measures, we mainly consider the unstructured and compound symmetry (or exchangeable), given that we have a relatively large sample size and equally spaced repeated measures. In practice, we will use the Akaike Information Criterion (AIC) to assess model fit and determine the best

covariance structure for the repeated measures. We will adjust for baseline BPI interference score, stratification variables including site, gender and prescription opioid use. We will relegate *post hoc* identified covariates that are imbalanced between groups for sensitivity analysis. For the first type of pairwise comparison (WHT vs. UPC and PC-GE vs. UPC), we will consider tests with  $p < 0.01$  to be significant. For the second type of pairwise comparison (WHT vs. PC-GE), we will consider tests with  $p < 0.03$  to be significant.

With the COVID-19 pandemic, treatment implementation may vary during the study period, and there may be incomplete adherence to the interventions and outcome assessments. We will collect additional time-dependent data to attempt to capture these fluctuations. The following is a list of variables we aim to collect:

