7.2 Primary Outcome

The primary outcome in this study is pain interference score of the BPI at 12 months. We will use all available data for a participant measured across baseline, 3-, 6-, 9- and 12-months. Hierarchical multi-level models (i.e. linear mixed-effects model), including treatment (WHT, PC-GE, UPC), time (categorical: 3-, 6-, 9- and 12-months), and the treatment by time interaction, and adjusting for the baseline value of the outcome and the stratification variables-site, gender, and current opioid therapy (yes/no), will be used. We will include a random intercept for participant and variance-covariance matrices to account for correlations within a participant and will use random effects to account for individuals nested within treatment (the IRGT nature of the trial). Pairwise comparisons will be made (the comparison WHT vs PC-GE at $\alpha=0.03$, WHT vs UPC at $\alpha=0.01$ and PC-GE vs UPC at $\alpha=0.01$), and we will estimate the

difference between arms at 12 months using a contrast. Least squares mean differences along with confidence intervals (97% for WHT vs. PC-GE; 99% for WHT vs. UPC and PC-GE vs. UPC) will be reported.

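### The fixed 0.03/0.01/0.01 split on the primary outcome is valid, but a gated closed test at the same 5% family-wise error is never less powerful and can win more pairs

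*SAP*

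**What the plan says.** The family is all three pairs of the three arms: "Three pairwise comparisons will be conducted: WHT vs. PC-GE; WHT vs UPC; PC-GE vs. UPC" (SAP 7.1). The same section sets the levels: "0.03 will be given to the comparison between WHT and PC-GE and 0.01 will be given to each of the comparisons" of an active arm with UPC. The sample-size section of the SAP states the error budget: "The overall family-wise type I error rate was set at 0.05 with a split of 0.03 for the WHT vs. PC-GE comparison", with 0.01 for each active arm against UPC. Protocol 8.6 agrees: "We will conduct two types of pair-wise comparisons with different alpha levels", followed by the same three values. SAP 7.2 repeats the levels for the 12-month contrast and matches the intervals to them: 97% for WHT vs PC-GE and 99% for the two comparisons with UPC.

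Neither document describes a closed, step-down, gatekeeping or recycling rule. The opening part of the SAP 7.1 sentence, "Overall, family-wise type I error rates (two-sided) of 0.05 will be considered for both the primary and secondary outcomes", extends the split to the secondary outcomes. SAP 7.3 handles those with a Benjamini-Hochberg procedure within each pair.

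On power, the SAP says "We assumed a power of 90% for all comparisons". For WHT vs PC-GE "we assumed 1:1 randomization and an effect size of 0.15", and for an active arm vs UPC it uses 0.3. The results are 273 evaluable per active arm and 50 in UPC.

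**The concern.** A plain weighted Bonferroni split treats the three pairwise nulls as if any combination of them could be true. With three arms that is not so, because no configuration has exactly two true pairwise nulls. The split therefore spends less than the allowed 5% whenever exactly one pair is equal. The unused part could go to the pairs that are hardest to win.

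The pair most exposed is PC-GE vs UPC. It has the small arm and a level of 0.01. If WHT beats PC-GE, as hypothesised, it also has the smaller of the two effects against UPC. Aim 1 hypothesises WHT better than PC-GE and both better than UPC, so support for the whole ordering would need all three tests.

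**Working it through.** **1. The plan's own figures.** The alpha sum is 0.03 + 0.01 + 0.01 = 0.05. The sample sizes reproduce only if the effect sizes 0.15 and 0.30 are Cohen's f (d = 2f = 0.30 and 0.60) and a single measure is used.

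- WHT vs PC-GE: n = 2(z₀.₉₈₅ + z₀.₉₀)²/d² = 2(2.170 + 1.282)²/0.30² ≈ 265 per arm. The exact F test gives 266, and power at 273 is 0.908.
- Active vs UPC: 273 against 50, d = 0.60, alpha 0.01, exact t test: power 0.904.

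**2. The closed test.** Gate: at least one of p(WHT vs PC-GE) ≤ 0.03, p(WHT vs UPC) ≤ 0.01, p(PC-GE vs UPC) ≤ 0.01. If the gate is passed, test each pair at two-sided 0.05.

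- All arms equal: an error requires passing the gate, with probability at most 0.05.
- Exactly one pair equal: only one false rejection is possible, and it requires p ≤ 0.05.
- Any pair rejected under the split passes the gate and has p ≤ 0.05, so it is still rejected.
- The event of at least one rejection is the gate itself, so its probability is unchanged.

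The argument needs only valid p-values for equality nulls. The random effects for the individually randomized group-treatment design do not alter it.

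**3. Simulated family-wise error (273/273/50, unit variance).**

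| Truth | Split | Closed |
|---|---|---|
| All arms equal | 0.044 | 0.044 |
| Only WHT = PC-GE | 0.030 | 0.050 |
| Only WHT = UPC | 0.010 | 0.050 |
| Only PC-GE = UPC | 0.010 | 0.050 |

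Testing all three pairs at 0.05 with no gate gives about 0.116 when all arms are equal, so the gate is essential.

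**4. Power, split to closed.** Completers are taken in three ways:

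- 273/273/50, the planned evaluable numbers.
- 282/282/51, from 769 enrolled, 11:11:2 and 20% attrition: 769 × 11/24 × 0.8 = 282 and 769 × 2/24 × 0.8 = 51.
- 273/273/66, from the stated 341/341/83: 341 × 0.8 = 273 and 83 × 0.8 = 66.

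Baseline adjustment multiplies the variance by 1 − 0.66² = 0.5644. Clustering is ignored throughout.

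| Completers, model | d vs UPC (WHT, PC-GE) | PC-GE vs UPC | All three |
|---|---|---|---|
| 273/273/50, single measure | 0.90, 0.60 | 90.7% to 97.4% | 82% to 91% |
| 282/282/51, baseline-adjusted | 0.90, 0.60 | 99.6% to 99.9% | 99.1% to 99.7% |
| 273/273/50, single measure | 0.60, 0.30 | 27% to 50% | 23% to 45% |
| 282/282/51, baseline-adjusted | 0.60, 0.30 | 52% to 75% | 52% to 74% |
| 282/282/51, baseline-adjusted | 0.45, 0.30 | 52% to 74% | 26% to 46% |
| 273/273/66, baseline-adjusted | 0.60, 0.30 | 63% to 83% | not tabulated |

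A hand check of the fourth row: the standard error is √[0.5644 × (1/282 + 1/51)] = 0.1143, so the expected z is 0.30/0.1143 = 2.62. Power at 0.01 is Φ(2.62 − 2.576) ≈ 0.52, and at 0.05 it is Φ(2.62 − 1.960) ≈ 0.75.

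The first two rows keep 0.30 between the active arms and 0.60 for PC-GE vs UPC, which puts WHT vs UPC at 0.90. The fifth row reads the plan's 0.15 and 0.30 directly as d.

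**The case against.** The split is valid, prespecified and the same in both documents, and the sample size and intervals are built on it. All of that stands. A reader might infer that the plan fails to control type I error, but the documents do not support this.

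A reader might also take a gain of about 23 points as the expected one. That figure sets PC-GE vs UPC at d = 0.30, half the 0.60 that reproduces the UPC requirement of 50, and Protocol 8.2 applies its effect size to both active arms. With the planned effects and baseline adjustment the gain in winning all three is under 1 point. The smaller effect is still possible: if WHT exceeds PC-GE, the two effects against UPC cannot both equal the planned value.

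Nor is winning all three a criterion for success. Aim 1 hypothesises the full ordering, but no section makes joint success a decision rule, and each pair is tested separately. WHT vs PC-GE, which drives the sample size, gains 3 points or less when it has about its planned 90% power or more.

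There is a cost in reporting. Each extra win has a p-value above its share, so its planned 97% or 99% interval will include zero. Relaxing thresholds after enrolment has ended (769 enrolled) also invites challenge. The SAP cover page allows edits up to data lock and before unblinding, but the documents do not say whether either has happened.

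**Conclusion.** The point holds as an optional efficiency gain for the primary outcome. The closed test keeps family-wise error at or below 0.05, loses no rejection made under the split, and leaves the chance of at least one significant pair unchanged.

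For winning all three pairs, the gain runs from under 1 point to about 23 points. The largest gains arise when PC-GE vs UPC has an effect near d = 0.30. The range rests on assumed effects, on 50 to 66 UPC completers, and on whether baseline adjustment delivers the variance reduction implied by a correlation of 0.66. The power figures ignore clustering and are illustrative. The error-control argument does not depend on them.

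It does not carry over to the secondary outcomes, because the proof concerns the three pairs of one outcome.

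**What to change.** If neither data lock nor unblinding has occurred, amend SAP 7.1 and 7.2 and Protocol 8.6 for the primary outcome only:

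- If at least one pair meets its level (0.03 for WHT vs PC-GE, 0.01 for each comparison with UPC), test each pair at two-sided 0.05. Otherwise reject none.
- State that the Benjamini-Hochberg rule in SAP 7.3 keeps its current levels. This has to be explicit because the SAP 7.1 sentence covers both sets of outcomes.
- Keep the 97% and 99% intervals and add 95% intervals labelled as not simultaneous.
- State that a pair won at a p-value between its share and 0.05 will have a planned 97% or 99% interval that includes zero.

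The cost is a few sentences in the SAP and a short protocol amendment, with no new data. The price is that test decisions and the planned intervals no longer correspond one to one. If lock or unblinding has passed, keep the fixed split.

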7.2 Primary Outcome

The primary outcome in this study is pain interference score of the BPI at 12 months. We will use all available data for a participant measured across baseline, 3-, 6-, 9- and 12-months. Hierarchical multi-level models (i.e. linear mixed-effects model), including treatment (WHT, PC-GE, UPC), time (categorical: 3-, 6-, 9- and 12-months), and the treatment by time interaction, and adjusting for the baseline value of the outcome and the stratification variables-site, gender, and current opioid therapy (yes/no), will be used. We will include a random intercept for participant and variance-covariance matrices to account for correlations within a participant and will use random effects to account for individuals nested within treatment (the IRGT nature of the trial). Pairwise comparisons will be made (the comparison WHT vs PC-GE at $\alpha=0.03$, WHT vs UPC at $\alpha=0.01$ and PC-GE vs UPC at $\alpha=0.01$), and we will estimate the

difference between arms at 12 months using a contrast. Least squares mean differences along with confidence intervals (97% for WHT vs. PC-GE; 99% for WHT vs. UPC and PC-GE vs. UPC) will be reported.

7.3 Secondary Outcomes

To control for false discovery for the secondary outcomes, we will use the Benjamini and Hochberg method¹⁵ for each of the pairwise comparisons with family-wise $\alpha=0.03$ for the comparison WHT vs PC-GE and family-wise $\alpha=0.01$ for the comparisons vs UPC. Secondary outcomes are pain intensity, total BPI, functioning, quality of life, use of high-risk pain medications (including opioids if applicable), number of nonpharmacological pain self-management activities, and co-morbid mental health-related symptoms (sleep, suicidality, depression, PTSD, anxiety, alcohol and substance use), and global impression of change. Like the primary outcome, we will use hierarchical multi-level models that include time, treatment, and the treatment by time interaction, and adjust for baseline value of the outcome, site, gender, and current opioid therapy. Random effects and variance-covariance structures will be used to account for repeated measurements within participants and the nesting of individuals within treatment group. Pairwise comparisons will be made using a contrast statement at the 12-month time point. For continuous outcomes, least squares mean differences and the appropriate confidence interval will be reported. For binary or count outcomes, generalized multi-level models will be used, and odds ratios and incident risk ratios will be reported with the appropriate confidence interval.

7.4 Exploratory Analyses/ Per Protocol Analyses

Responder analysis (exploratory analysis). Response will be defined as at least a 30% improvement in BPI interference score from baseline. Reduction in pain/interference of this size has been found to be clinically meaningful and IMMPACT recommended that the percentage of participants with this reduction be reported in chronic pain clinical trials.¹⁶ In addition, they recommended the percentages of patients with at least 50% improvement (substantial improvement) also be reported. We will also report the number who achieved a reduction in pain interference of at least 1 point (minimal clinically important difference for BPI interference).

With the COVID-19 pandemic, treatment implementation may have varied during the study period, and there may have been incomplete adherence to the interventions and outcome assessments. We collected additional time-dependent data to attempt to capture these fluctuations (variables such as mode of treatment delivery, availability of pain management services, and COVID infection status). Our strategies are to: (1) adjust for time-dependent variables that reflect changes in the implementation of treatments, and (2) perform analyses using interactions to see whether the treatment effect differs by time periods, sites, and site characteristics such as degree of availability of pain management services. Inherently these will have limited power, and no further adjustments will be made for multiple testing given the exploratory nature of these analyses.

Additional analyses will consider a per protocol population and repeat the primary analysis in this population. In the per protocol population, we will include any subject who minimally or completely adhered to treatment assignment indicated by the protocol, but will exclude the protocol violators who did not meet the following minimal threshold criteria: if randomized to the WHT arm, participants attended at least 6/8 coaching sessions, the WHT initial visit, and at least 2 of 3 follow-up WHT visits; if randomized to the PC-GE arm, participants attended the orientation and at least 4 of 5 core modules. In addition, participants will be excluded from the per-protocol analysis if they received prohibited concomitant interventions or if they missed all outcome measurements.

We will follow recommendations by Hernan and Robins¹⁷ and also adjust analyses for post-randomization prognostic factors of adherence. We will examine if the post-randomization prognostic factors are affected by prior treatment. If so, we will use the inverse-probability weighting method. This entails estimating a sequential propensity score based on post-randomization time-dependent factors and reweighting subjects using the propensity score estimated earlier. This method helps us minimize post-randomization confounding and selection bias.

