The COVID-19 pandemic requires even greater pragmatism with respect to intervention delivery. Telehealth resources reflect an alternative way of delivering care when in-person care delivery may not be feasible or available, such as with the COVID-19 pandemic. Some participants may be less willing or able to use telehealth than others and thus with shelter-in-place orders or phased recovery plans, COVID-19 may impact subjects' ability to remain engaged in the study interventions and provide outcomes data. On the other hand, with more and more veterans learning to use telehealth and prohibitions on travel and relocation, more veterans may complete the study interventions and the follow-up assessments, providing outcomes data. Thus, given the unknown impact of COVID-19 pandemic on participants and study outcomes, we will need to plan for the possibility that a per-protocol analysis may be needed in addition to the planned intention-to-treat analysis (ITT). As opposed to the ITT analysis which includes all participants who were enrolled and randomized to one of the three study interventions, the per-protocol analysis includes only subjects who completed the protocol of the originally allocated treatment. This per-protocol effect is the maximum potential benefit of the active treatments and is estimated without being affected by incomplete adherence; therefore, the per protocol analysis may be of more interest for patients who consider whether to use the intervention. If using per-protocol analysis the effect size of a COVID-19 period is attenuated compared with that of a non-COVID period, we can infer that COVID-19 may have mitigated the effect of the intervention for a variety of reasons; e.g., telehealth vs. in-person intervention delivery; lack of available pain resources in VA or the community etc. On the other hand, if it is feasible to conduct both ITT and per-protocol analyses, and if the results agree, we can conclude that COVID-19 had limited influence on the treatment effects. In summary, we expect more pragmatic features in the "organization" and "primary analysis" domains of the PRECIS-2 Tool due to the impact of COVID-19.

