## Usual Primary Care

In VA, patient-aligned care teams (PACTs) or primary care is step 1 of VA's Stepped Care Model in the treatment of chronic pain. PCPs are expected to possess the requisite skill set for management of common chronic pain-causing conditions, which includes biopsychosocial assessment, multi-modal treatment, and coordination of specialty pain care after shared-decision making that incorporates patient preferences and values. Participants randomized to this arm will continue to have their PCP and PACT serve in this role. All participating PCPs/PACT members will have been oriented to the web-based/mobile WHRD and can use this to identify CIH pain-related resource at VA and in the community for their patients who are enrolled as study participants. Study visits will be captured through use of VA administrative data as each of the clinics will be mapped to clinic stop codes denoting the research study as well as the mode of care delivery (in-person, video telehealth, or telephone).

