System-level variables: sites' degree of openness (fully closed/partially open/fully open (categorical), mode of treatment delivery (in-person, tele-health, phone, categorical), availability of non-pharmacologic pain management services (Yes/Partially yes/No, categorical); Individual-level variables: COVID infection status (categorical: yes, no, unknown), self-reported socio-economic outcomes such as lack of access to transportation, food, prescription refills, and community resources (categorical), health outcomes such as mental health and pain (categorical), number of missed intervention sessions. (numerical).

For the issues of fluctuations in mode of treatment delivery and temporal variations, our strategies are to: (1) adjust for time-dependent variables that reflect changes in the implementation of treatments, and (2) perform an exploratory analysis stratified by time periods sites, and site characteristics such as degree of openness. The exploratory analysis has an inherent limitation of inadequate power, because the analytical sample will be partitioned by time periods and sites.

We will also consider a per-protocol analysis to supplement the ITT analysis. This analysis includes only patients who minimally or completely adhered to treatment assignment indicated by the protocol, but will exclude the protocol violators who did not meet the following minimal threshold criteria: if randomized to the WHT arm, participants attended at least 6/8 coaching sessions, the WHT initial visit, and at least 2 of 3 follow-up WHT visits; if randomized to the PC-GE arm, participants attended the orientation and at least 4 of 5 core modules. In addition, participants will be excluded from the per-protocol analysis if they received prohibited concomitant interventions or if they missed all outcome measurements. We will follow recommendations by Hernan and Robins and adjust for both pre-randomization (baseline) and post-randomization prognostic factors. We will examine if the post-randomization prognostic factors are affected by prior treatment. If so, we will use the inverse-probability weighting method. This entails estimating a sequential propensity score based on post-randomization time-dependent factors and reweighting subjects using the propensity score estimated earlier. This method helps us minimize post-randomization confounding and selection bias.

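### The exploratory COVID-19 adjustment leaves post-randomisation variables open as covariates, and Protocol 4.3 draws an invalid conclusion from ITT/per-protocol agreement

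*SAP*

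**What the plan says.** SAP 7.4 gives two strategies for pandemic-related variation. Strategy (1) is to "adjust for time-dependent variables that reflect changes in the implementation of treatments". Strategy (2) tests whether the treatment effect differs by period, site and site characteristics. The data collected for this purpose are described by example: "variables such as mode of treatment delivery, availability of pain management services, and COVID infection status". The SAP calls these analyses exploratory and of limited power.

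Protocol 8.6 has the same strategy (1), introduced by "For the issues of fluctuations in mode of treatment delivery and temporal variations, our strategies are to". Its list of time-dependent data to be collected is longer. At system level it has site openness, delivery mode and service availability. At individual level it has COVID infection, socio-economic items, and "health outcomes such as mental health and pain (categorical), number of missed intervention sessions".

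Protocol 8.6 and SAP 7.4 both plan, for the per-protocol analysis, to examine whether post-randomisation prognostic factors are affected by earlier treatment and, if so, to use inverse-probability weighting.

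Protocol 4.3 compares the ITT and per-protocol analyses and states: "if the results agree, we can conclude that COVID-19 had limited influence on the treatment effects". The SAP does not repeat this.

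The primary model in SAP 7.2 adjusts only for baseline score, site, gender and opioid therapy.

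**The concern.** A covariate that arises after randomisation can be changed by the arm, or can be related to prognosis through the participant's own choices. Putting it in the outcome model means the arm coefficient no longer estimates the effect of being assigned to that arm, and it may be biased for any other effect as well. The plan acknowledges this for the per-protocol analysis but has no matching check for strategy (1), and it does not close the list of adjusters.

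The sentence in Protocol 4.3 is a separate problem. It takes a comparison that is informative about adherence and uses it to answer a question about the pandemic.

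At stake are a pandemic-adjusted contrast that could be published without a clear meaning, and a statement that COVID-19 mattered little which the data could not support. The confirmatory result is not at stake.

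**Working it through.** No figure in the documents rests on this point, so there is none to reproduce. The check compares the texts and adds one piece of algebra with assumed values.

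**1. Is delivery mode independent of arm?**

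- WHT: team visits may be in person, by video or by telephone, but coaching sessions are by telephone or video only (Protocol 6.1, WHT coaching protocol).
- PC-GE: sessions may be attended in any of the three modes (Protocol 6.1, PC-GE elements).
- UPC: mode is to be captured through clinic stop codes (Protocol 6.1, Usual Primary Care). It exists, but describes usual care rather than a study intervention.

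Mode is therefore partly set by arm, and for UPC it measures something different. Neither document says from which contacts a participant's mode is to be derived.

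**2. What does adjustment do to the contrast?** In a linear model for two arms,

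adjusted contrast = total contrast − a × b,

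where a is the arm difference in the covariate and b its within-arm association with the outcome. For delivery mode, b mixes any effect of mode with differences between the participants who choose each mode. The documents give neither a nor b, and the sign of b is open, so neither direction nor size follows. If mode were taken only from contacts where WHT and PC-GE offer the same choices, a could be small. For COVID infection, nothing in the documents says that arm changes it, so a may also be small.

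**3. Which variables can enter strategy (1)?** The SAP's list is illustrative. Protocol 8.6 lists missed sessions, pain and mental health as data to collect, not expressly as adjusters; nothing excludes them. Missed sessions are not defined for UPC. Pain intensity and mental health symptoms are secondary outcomes of the trial (Protocol 8.5.2, SAP 7.3).

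**4. Does ITT/per-protocol agreement measure COVID-19 influence?** Inputs:

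- variance 5.90 (Protocol 8.2), so SD = √5.90 = 2.429
- assumed effect without COVID-19: D = 0.30 SD = 0.30 × 2.429 = 0.729 BPI points
- assumed share of adherers p = 0.70
- assumed fraction of the effect reaching non-adherers: k
- assumed share of the effect that COVID-19 removes, equal in everyone: c

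Formulas: per-protocol = D(1 − c); ITT = D(1 − c)[p + (1 − p)k].

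With k = 0.5 the bracket is 0.70 + 0.30 × 0.5 = 0.85:

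| c | per-protocol | ITT | gap |
|---|---|---|---|
| 0 | 0.729 | 0.619 | 0.109 |
| 0.25 | 0.547 | 0.465 | 0.082 |
| 0.50 | 0.364 | 0.310 | 0.055 |
| 0.75 | 0.182 | 0.155 | 0.027 |

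The ratio ITT/per-protocol is 0.85 in every row, because c cancels. The absolute gap narrows as the harm grows. With k = 1 the two estimates are equal at every c.

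Disagreement is no better a guide. If adherers also have a better prognosis by 0.15 SD (assumed; 0.15 × 2.429 = 0.364 points), the gap at k = 0.5 is 0.109 + 0.364, about 0.47, with no COVID-19 effect at all.

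**The case against.** The strongest reply is that the plan says less than a critic might read into it. Strategy (1) concerns implementation of treatment, and a participant's pain or mood is not that. Protocol 8.3 ties the time-dependent COVID-19 data to incomplete adherence and post-randomisation confounding in the per-protocol analysis, and the summary in Protocol 8.6 says that collecting them makes that analysis possible. The work is exploratory, the interactions that answer the question are already strategy (2), and Protocol 8.6 refers to the Data Analysis Plan for the full analysis, which omits the agreement sentence. Protocol 4.3 also compares COVID with non-COVID periods, which is a relevant comparison.

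Much of this stands, and it rules out three stronger readings that a reader might infer:

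- *That the plan adjusts for pain, mental health and missed sessions and so loses 50–70% of the effect.* The arithmetic is d_Y − r × d_M: with 0.30 for both effects and r of 0.5 to 0.7, 0.30 − 0.15 = 0.15 and 0.30 − 0.21 = 0.09. But r and d_M are assumed, and the covariate is a concurrent pain item that the SAP does not name.
- *That delivery mode is undefined in UPC.* The protocol plans to capture it; comparability is the issue.
- *That the coefficients cannot be separated from arm.* Mode and missed sessions vary within WHT and within PC-GE, which identifies them. What changes is the meaning of the UPC contrast, which then refers to a chosen reference level.

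The reply does not remove two things. Delivery mode is named, is post-randomisation and is partly set by arm, and strategy (1) has no safeguard. The agreement sentence remains in the current protocol.

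**Conclusion.** The point holds in limited form and is worth correcting. Strategy (1) permits outcome-model adjustment for post-randomisation implementation variables, with an open list and without the check applied to the per-protocol analysis. For delivery mode this changes the estimand and can bias the contrast, by an amount and in a direction that the documents do not determine. Missed sessions, pain and mental health are a risk only because nothing excludes them.

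The inference in Protocol 4.3 is invalid however strategy (1) is read. Both estimates use the same pandemic-period participants. Agreement can suggest that non-adherence mattered little, including non-adherence caused by the pandemic; it says nothing about loss of effect among those who adhered. The table in the working illustrates this under assumed values and a uniform COVID-19 loss. It does not estimate what happened in this trial.

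The primary ITT analysis and its alpha split are unaffected.

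**What to change.** In SAP 7.4 and Protocol 8.6:

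- Replace the open list in strategy (1) with a closed one, restricted to variables fixed at randomisation or external to the participant: calendar period, and site openness or service availability recorded by site and date.
- Use delivery mode, missed sessions, COVID infection and self-reported pain or mental health only in the weight models of the per-protocol analysis.
- Answer the COVID-19 question with the interactions already planned as strategy (2), and add site openness, which Protocol 8.6 names but SAP 7.4 does not.

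In Protocol 4.3, delete the sentence on agreement between the ITT and per-protocol results. The comparison of COVID with non-COVID periods can stay.

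The cost is wording only; no new data are needed. What is lost is a mode-adjusted exploratory estimate. The SAP's front page allows changes up to final data lock and before unblinding; the documents do not say whether that point has passed.
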